PROVESA trial

Proficiency based progression training for robotic vesico-urethral anastomosis chicken model versus the Halsted's model: a cross-specialty, multicentric, randomized and blinded clinical trial.

Study Protocol

Principal Investigator: [name] [name]

Research center: ORSI Academy, Melle, Belgium

July 27th 2020

NCT ID not yet assigned

Ethical Committee approval number 22072020

Summary

In a prospective, randomized and blinded study robotic naïve (urology ($n = 12$), surgery ($n = 12$) and gynecology ($n = 12$)) residents ($n = 36$) from the KU Leuven and University of Gent residency training programs will be randomized (in equal discipline numbers) to Traditional Halstedian apprenticeship type training or proficiency based progression (PBP) training to learn to perform a vesico-urethral anastomosis (VUA) on a chicken model. Both groups will receive the same e-learning (on how to perform the VUA on the chicken model) and skills laboratory robotic training curriculum. The PBP trained group will however be required to demonstrate quantitatively defined proficiency benchmarks for training progression (i.e., from e-learning to the skills lab). The PBP group will also have a defined benchmark to demonstrate before training is deemed completed. The Traditional trained group will train in the same skills laboratory for a case-matched period of time as the PBP group, with the same level of supervising faculty proctors and using the same training resources but with no proficiency benchmarks or metric-based feedback. Both groups will be required to perform a VUA on the chicken model before skills training proper and at the end of training. Investigators will be trained in pairs to assess VUA performance from a pre-defined set of explicitly defined binary metric events reliably (inter-rater reliability > 0.8). They will also be blinded as to the identity of the trainee performing the procedure, how they were trained (i.e., group) and procedure order.

H₁ It is hypothesised that implementation of PBP training in teaching the robotic suturing of VUA leads to better surgical training outcomes (i.e., lower number of performance errors) when compared to Halsted's method.

Proficiency based progression training for robotic vesico-urethral anastomosis chicken model versus the Halsted's model: a prospective, randomized and blinded clinical trial.

Introduction

Current surgical training is outdated.¹ The Halsted's model 'See one, Do one, Teach one', is still widely used during training of surgeons. Consequently, a patient is still exposed to a novice resident who does the procedure for the very first time. For too long, surgical training is dependent on the quality of the trainer with a lack of systematics, standardization and objective scoring systems.² Because of financial and ethical reasons, it can no longer be justified that the beginning of a learning curve takes place in the operating room on real life patients. By mitigating the initial learning curve in an out-of-hospital setting and by developing a standardized, novel training system, patient safety could be improved.

Proficiency Based Progression (PBP)³⁻⁵ training or Quality Assured Training is a novel training method that already has demonstrated its value in different surgical specialties.⁶⁻¹² In this kind of training a specific level of performance defined by a quantitative score (benchmark) or scores on a standardized assessment must be demonstrated to gain the proficiency level. Only demonstrating the ability to meet quantitatively defined performance benchmarks permits progression in training (i.e., proficiency-based progression [PBP] training).

Background

Suturing and knot tying are fundamental skills for all surgical disciplines. They serve an important clinical function but using a minimally invasive approach means that they are even more challenging to complete. A curricular approach to learning laparoscopic suturing and knot tying has been successfully demonstrated for Nissen fundoplication.¹⁰

Fundamental in creating a proficient robotic surgeon is the acquisition of basic surgical skills, such as suturing and knot tying.¹³ Some training models mimic the real anatomical environment in which a procedure will be performed and provide trainees with the opportunity to learn and practice their skills before starting their practice on real cases in the operating room. Numerous dry-lab, wet-lab, and virtual reality simulation models have been described.¹⁴ The "Venezuelan chicken model" is generally accepted as a optimal model for trainees to learn robotic suturing, anastomosis and knot tying tasks (for all surgical disciplines).¹⁴⁻¹⁶ We will use the Venezuelan chicken model in this study. It has several advantages; it is inexpensive, widely available, easy to prepare, it is a good model for the urethro-vesical anastomosis training, it is possible to introduce a catheter and performing the leakage test, it takes the trainee approx. 20 mins to complete the task. Over the past 12 months ORSI has developed and validated (Delphi consensus and Construct Validity) performance metrics for the task.

This study aims to compare the effectiveness of Halsted's apprenticeship approach to training with the Proficiency Based Progression (PBP) approach for teaching the robotic suturing of a vesico-urethral anastomosis (VUA) on a chicken model.

Methods

Subjects

Robotic naïve urology ($n = 12$), surgery ($n = 12$) and gynecology ($n = 12$) residents ($n = 36$) from the UKU Leuven and University of Gent residency training programs will participate. They will be randomized (using an online randomizer <https://www.random.org/>) to teaching of VUA suturing with either Halsted's ($n = 18$) or the PBP method including procedure-specific, validated metrics ($n = 18$).

Procedure and training

Trainees in the Traditional trained group will be trained according to the traditional approach of 'See one, do one, teach one' principle. Trainees will have a e-learning didactic component (specifically on the anatomy & physiology of the procedure, clinical aspects of the procedure, published evidence etc) which they must complete before training by a procedure expert. On completion of the e-learning module they will complete a summative assessment of their knowledge. They will then be shown how and then trained to suture and tie knots using the robot. The VUA will be demonstrated initially by an expert and who will then proctor the trainees in the same technique for repeated training trials., i.e., repeated practice for a period of time matched to the PBP group.

Students in the PBP trained group will follow the exact same e-learning didactic course as the Traditional trained group but the PBP group will be required to pass a test of procedure knowledge before continuing to the surgical training. Their knowledge will be assessed in a formative and summative fashion. After their initial VUA assessment, procedure-specific and validated procedure metrics will be used to teach the students the steps of the procedure, as well as the correct (and incorrect) way to perform the procedure. The metrics will be used to give them performance feedback with specific advice on how they might improve their performance, i.e., deliberate practice.¹⁷

Both groups of subjects will receive the exact same amount of training and have access the same didactic and training resources. Both groups will also complete a baseline assessment on the chicken model before technical skills training. Assessors, blinded to group membership and procedure order (first or last procedure) will evaluate each student's first and final VUA with the validated chicken anastomosis metrics. They will also assess performance with the GEARS¹⁸ assessment tool (Figure 2). Additionally, the student's satisfaction of the training method will be assessed using a Likert scale 1-5 (Figure 3).

Proficiency Definition: In the study proposed here proficiency levels will be quantified and defined on the objectively assessed performance of surgeons experienced in performing that VUA task being trained. This performance level will be established from the construct validation study of the procedure metrics derived from the procedure characterizations.^{4, 5, 19}

Performance assessments

Investigators will be trained in pairs to assess performance from a pre-defined set of explicitly defined metric events reliably (inter-rater reliability > 0.8). They will be blinded as to the identity of the trainee performing the procedure, how they were trained (i.e., group) and procedure order.

Procedure performance assessment

[figure not shown]
We will record how long subjects took to perform the procedure, the number of steps correctly completed and procedure errors/deviations from optimal performance. We will also record and cost the instrumentation/needles/suture etc utilised in the performance of the procedure.

Baseline Assessment: -Prior to the commencement of education and training protocol all subjects from both groups will be assessed on their performance of the VUA task. Performance on the procedure will be video recorded and assessed as previously described.

Statistical Analysis: From previous similar studies, it has been found that data has been reasonably normally distributed and suitable for parametric statistical analysis. If the data violates any of the assumptions of normality, data will be compared for statistical significance with Mann-Whitney U for comparison between two independent samples and Wilcoxon signed-rank test. Where data are normally distributed with approximately equal variance differences between groups, task performance will be compared for statistical significance with two-factor Analysis of Variance where factor one is the type of training subjects received and factor two is the order the task was performed (i.e, baseline

performance and end of training performance). The same analysis will be used to assess the binary checklist metric scores and the GEARS scores (seperately) for the Standard trained and the PBP trained groups. Specific post hoc statistical contrasts between surgeon groups performance within a training condition (i.e., between the objectively assessed performance of urology, surgery and gynecology residents) will be done with Scheffe F-tests.

Statistical power calculation: A pilot study has shown that novices on average make 16.6 (SD = 4) performance errors on the task. Assuming a reduction of ~40% with PBP training (i.e., 16.6 vs 10 errors) with a standard deviation of n = 4, an Alpha – 1% with 16 subjects in each group would yield a statistical power of 0.998 for the proposed study.

* By assessors blinded to group membership and procedure order (first or last procedure)

** Matching according to specialty

Figure 1. the design of the prospective randomized study to evaluate the impact of PBP on learning the robotic surgical skills for a vesico-urethral anastomis (VUA) on a chicken model.

Hypothesis

- H₁ Implementation of PBP training in teaching the robotic suturing of VUA leads to better surgical training outcomes (i.e., lower number of performance errors) when compared to Halsted's method.
- H₀ There will be no difference in the procedure knowledge prior to VUA training
- H₀ There will be no difference in the objectively assessed procedure performance of the urology, surgery and gynecology residents at the end of training in the PBP group
- H₀ There will be a difference in the objectively assessed procedure performance of the urology, surgery and gynecology residents at the end of training in the Traditional trained groups.
- H₀ There will be no difference in student satisfaction with the two approaches to training.

Depth perception				
1	2	3	4	5
Constantly overshoots target, wide swings, slow to correct		Some overshooting or missing of target, but quick to correct		Accurately directs instruments in the correct plane to target
Bimanual dexterity				
1	2	3	4	5
Uses only one hand, ignores nondominant hand, poor coordination		Uses both hands, but does not optimize interaction between hands		Expertly uses both hands in a complementary way to provide best exposure
Efficiency				
1	2	3	4	5
Inefficient efforts; many uncertain movements; constantly changing focus or persisting without progress		Slow, but planned movements are reasonably organized		Confident, efficient and safe conduct, maintains focus on task, fluid progression
Force sensitivity				
1	2	3	4	5
Rough moves, tears tissue, injures nearby structures, poor control, frequent suture breakage		Handles tissues reasonably well, minor trauma to adjacent tissue, rare suture breakage		Applies appropriate tension, negligible injury to adjacent structures, no suture breakage
Autonomy				
1	2	3	4	5
Unable to complete entire task, even with verbal guidance		Able to complete task safely with moderate guidance		Able to complete task independently without prompting
Robotic control				
1	2	3	4	5
Consistently does not optimize view, hand position, or repeated collisions even with guidance		View is sometimes not optimal. Occasionally needs to relocate arms. Occasional collisions and obstruction of assistant.		Controls camera and hand position optimally and independently. Minimal collisions or obstruction of assistant

Figures 2. The GEARS assessment tool

TRAINING EVALUATION FORM

Course name: _____
 Instructor: _____
 Date: _____

Training Quality					
The overall quality of the training I received was high	Strongly Disagree	Disagree	Neutral	Agree	Strongly Agree
This training will be beneficial to me in the performance of my job	Strongly Disagree	Disagree	Neutral	Agree	Strongly Agree
Course Presentation					
The methods of content delivery (lectures, PowerPoints, etc.) were appropriate for this course.	Strongly Disagree	Disagree	Neutral	Agree	Strongly Agree
The course material was easy to understand and helpful.	Strongly Disagree	Disagree	Neutral	Agree	Strongly Agree
The topics were presented in a logical order.	Strongly Disagree	Disagree	Neutral	Agree	Strongly Agree
The vocabulary used in the course was clear and easy to understand.	Strongly Disagree	Disagree	Neutral	Agree	Strongly Agree
The instructor was knowledgeable and effective.	Strongly Disagree	Disagree	Neutral	Agree	Strongly Agree
Course Objectives					
The course covered the material I expected.	Strongly Disagree	Disagree	Neutral	Agree	Strongly Agree
The times scheduled for the agenda items were appropriate.	Strongly Disagree	Disagree	Neutral	Agree	Strongly Agree
The course met the training objectives.	Strongly Disagree	Disagree	Neutral	Agree	Strongly Agree
The course met my training needs.	Strongly Disagree	Disagree	Neutral	Agree	Strongly Agree

Figure 3: Likert-scale for the assessment of training satisfaction

References

1. Pellegrini CA. Surgical education in the United States: navigating the white waters. *Annals of Surgery* 2006; 244(3):335 - 342.
2. Cuschieri A. Whither minimal access surgery: tribulations and expectations. *The American Journal of Surgery* 1995; 169(1):9 - 19.
3. Gallagher A. Metric-based simulation training to proficiency in medical education:- What it is and how to do it. *Ulster Medical Journal* 2012; 81(3):107-113.

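### Allocation is balanced on specialty only, although residents come from two university programmes, and the unstated time of randomisation leaves open that the baseline VUA depends on the arm

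*Combined protocol and SAP*

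**What the plan says.** **Balancing factor.** The Summary states that residents "from the KU Leuven and University of Gent residency training programs will be randomized (in equal discipline numbers", and the Figure 1 footnote adds "Matching according to specialty". Methods, Subjects gives only the tool: "They will be randomized (using an online randomizer". It sets 12 residents in each of three specialties and 18 per arm, hence 6 per arm in each specialty. The title calls the trial multicentric. The Statistical Analysis paragraph uses a two-factor ANOVA with training type and task order (baseline or end of training) as factors. University does not appear in it.

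**Timing of baseline.** The Baseline Assessment paragraph says: "Prior to the commencement of education and training protocol all subjects from both groups will be assessed on their performance of the VUA task". Procedure and training says: "Both groups will also complete a baseline assessment on the chicken model before technical skills training". The Summary likewise has both groups perform the VUA before skills training proper. Procedure and training describes the knowledge test that only the PBP group must pass before it mentions that group's initial VUA.

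**Blinding.** The Summary, Procedure and training, and Performance assessments describe blinding of assessors. No blinding of trainees is stated. The moment of randomisation is not given in the readable text, and the Figure 1 diagram is not shown.

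**The concern.** Two matters are left open that could be settled when the list is drawn.

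- **University.** Residents from two programmes may differ in earlier suturing exposure. With 6 residents per arm in each specialty, specialty-only balancing leaves the university mix to chance. A difference between programmes then enters the comparison of final errors as avoidable noise.
- **Baseline.** Baseline is one level of the order factor, so anything that makes it differ by arm goes straight into the training-by-order contrast. If residents know their arm at baseline, effort may differ. If the PBP-only knowledge test comes first, PBP residents may also be better prepared. A resident who withdraws after learning the allocation but before baseline leaves no data at either time point.

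**Working it through.** **Inputs from the documents.** 12 residents per specialty, 6 per arm in each; 18 per arm; 16.6 versus 10 errors (difference 6.6); SD 4; alpha 1%, sidedness not stated.

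**Assumed inputs, not in the documents.** University split within specialty; university effect of 1 to 3 errors at the final VUA; baseline-to-final correlation (rho) of 0.3 to 0.7; arm-related baseline shift of 1 error.

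**1. The plan's power figure.** The plan gives 0.998 for 16 per group at alpha 1%. The exact t-test gives 0.966 two-sided and 0.983 one-sided; the normal approximation gives 0.982 and 0.990. A value of 0.998 appears at one-sided 5% (t-test 0.9982). Nothing below depends on this figure. The reference used here is 18 per arm, two-sided 1%, exact t: 0.983.

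**2. University imbalance under specialty-only balancing.** In each specialty, the number of PBP residents from one university is hypergeometric (12 residents, L from that university, 6 drawn). The three specialties are summed by exact convolution. The between-arm difference is |2X − 3L|, where X is the total in the PBP arm.

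| Split in every specialty | P(difference ≥ 4) | P(difference ≥ 6) |
|---|---|---|
| 6/6 | 0.332 | 0.105 |
| 8/4 | 0.304 | 0.084 |
| 9/3 | 0.133 | 0.022 |
| 10/2 | 0.193 | 0.023 |
| 11/1 | 0 | 0 |

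The 9/3 and 11/1 totals (27 and 33) are odd, so only odd differences can occur, which is why 9/3 lies below 10/2. With 6/6 the SD of the difference is 3.13 residents, and 25.3% of allocations are exactly even.

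**3. Effect on the final-score contrast.** Shift = (imbalance / 18) × university effect.

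- Imbalance 6, effect 1: 6/18 × 1 = 0.33 errors (0.33/6.6 = 5%). Power 0.971.
- Imbalance 6, effect 2: 6/18 × 2 = 0.67 errors (10%). Power 0.951.
- Imbalance 6, effect 3: 6/18 × 3 = 1.0 error (15%). Power 0.922.

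The power values apply when the shift is against PBP. At one SD of imbalance, effects of 1 to 3 errors give 3.13/18 × 1 = 0.17 to 3.13/18 × 3 = 0.52 errors. A university effect of equal size at both VUAs would cancel from the change contrast.

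**4. Effect of an arm-related baseline shift.** The training-by-order contrast is the between-arm difference in change. The SD of change is 4 × √(2(1 − rho)), and the standard error is that SD × √(2/18), i.e. SD/3. A baseline shift of 1 error biases the contrast by 1 error (1/6.6 = 15%). With no true effect, a two-sided 1% test on 34 df rejects as follows.

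| rho | SD of change | Standard error | Rejection rate |
|---|---|---|---|
| 0.3 | 4.73 | 1.58 | 2.5% |
| 0.5 | 4.00 | 1.33 | 3.2% |
| 0.7 | 3.10 | 1.03 | 4.9% |

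A comparison of final scores alone does not use baseline and is unaffected.

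**5. After the change.** With even strata, the university difference between arms is 0. With odd strata in all three specialties (for example 7/5), each contributes a difference of 1: the total is 3 if all are rounded the same way and 1 if the rounding alternates. Allocation after baseline removes any effect of allocation on baseline by design.

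**The case against.** The case for leaving the plan alone has several parts.

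- **Specialty is a defensible single stratifier.** It is the factor that the secondary hypotheses concern, and 36 residents is a small number. All residents are robotic naïve and train in the same skills laboratory, so university is where they come from, not a training site. This stands as a reason to keep the point modest. It does not explain leaving out a characteristic that is known in advance and costs almost nothing to balance.
- **The imbalance is chance and small.** This stands. A reader might infer that the arms will be biased by university. The documents do not support that: randomisation leaves no systematic direction, no figure shows a university effect, and the split is unknown. Quoting only the 33% would also mislead, since some splits give far less.
- **Speaking of both groups at baseline may only mean everyone.** This stands in part. A reader might infer that residents are certainly allocated, and aware of it, before baseline. No section says so, and Figure 1 might place allocation afterwards. Equally, no section says that allocation waits or is withheld from trainees.
- **Nothing shows that trainees would hold back at baseline.** True; the 1-error shift is illustrative. A 5% test would give a larger false-positive rate, but the only alpha in the plan is 1%.
- **Randomising after baseline is more than redrawing a list.** This stands. If baseline follows the e-learning and the PBP-only test, arms must exist before it, and the sequence itself has to be settled.

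**Conclusion.** The point holds as an inexpensive improvement, not as a threat to the trial's conclusion.

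- **Firm on the text:** specialty is the only balancing factor, university is absent from the analysis, the time of randomisation is unstated, and the sections disagree on whether baseline precedes all education or only the technical skills training.
- **Conditional:** that baseline may depend on the arm. If Figure 1 places allocation after baseline, this part reduces to a matter of wording; the university part does not depend on the figure.
- **Size, on assumed inputs:** a university difference between arms of 4 or more residents in 0% to 33% of allocations, depending on the split. In the least favourable case worked (6-resident imbalance, 3-error effect), power falls from 0.983 to 0.922. For a 1-error baseline shift, the false-positive rate of the change contrast is 2.5% to 4.9% in place of 1%.

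**What to change.** 1. Reconcile the Summary, Procedure and training, and Baseline Assessment so that the baseline VUA precedes every arm-specific step, as the Baseline Assessment paragraph already has it.
2. State when randomisation takes place, and draw the list only after the baseline VUAs have been recorded.
3. Randomise 1:1 within specialty by university (six strata), keeping 6:6 in each specialty. Where strata are odd, alternate the rounding across specialties.
4. Add university as a one-degree-of-freedom fixed term in the comparison of errors between arms.

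The cost is one degree of freedom, a small residual imbalance where strata are odd, and a commitment to a fixed order of baseline and e-learning. No additional residents or staff are needed, and the sample size is unchanged.

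### Does the plan need a rule for the final VUA when a PBP resident never meets the completion benchmark?

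*Combined protocol and SAP*

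**What the plan says.** The PBP arm finishes on performance, not on time. The Summary states: "The PBP group will also have a defined benchmark to demonstrate before training is deemed completed". The Introduction gives the general principle: "Only demonstrating the ability to meet quantitatively defined performance benchmarks permits progression in training". No number of hours or attempts is given.

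The Traditional arm has no duration of its own. The Summary says "The Traditional trained group will train in the same skills laboratory for a case-matched period of time as the PBP group". The Procedure and training section describes "repeated practice for a period of time matched to the PBP group" and adds: "Both groups of subjects will receive the exact same amount of training".

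On assessment, the Summary says: "Both groups will be required to perform a VUA on the chicken model before skills training proper and at the end of training". Under Procedure and training, assessors "blinded to group membership and procedure order (first or last procedure) will evaluate each student's first and final VUA". The Statistical Analysis paragraph compares baseline with end-of-training performance in a two-factor analysis of variance.

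Figure 1, the design diagram, could not be read in the text used for this review. Its surviving footnotes say only that assessors are blinded and that matching is by specialty.

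**The concern.** If a PBP resident does not reach the benchmark, nothing in the readable text ends that resident's training. Traditional time is borrowed from PBP time, so the gap reaches both arms, whether matching is by resident, by specialty or by group. The time of the final VUA would then be settled during the trial. Only the assessors are described as blinded, so those settling it could know the allocation.

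A second worry is that the VUA is at once the baseline test, the practice task and the final test, and the scored procedures are identified by order. If PBP training stops on the attempt that met the benchmark, that attempt could be taken as the last procedure. A score chosen because it was good would then be compared with an unselected Traditional score. Leaving out residents who never qualified would also favour PBP. Blinded rating would cure neither problem, because the selection happens before the video is rated.

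A smaller version of the worry concerns the knowledge hypothesis. PBP residents have to pass a test and Traditional residents only have to take one, and the attempt to be compared is not named.

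At stake is the number of errors at the end of training, on which H1 rests.

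**Working it through.** **1. The plan's own figure.** The power paragraph gives 16.6 versus 10 errors (difference 6.6), SD 4, alpha 1%, 16 per group and power 0.998. The noncentrality is 6.6 / (4 × √(2/16)) = 4.667. At two-sided 1% this gives power 0.982 by the normal approximation and 0.966 by the exact t-test. One-sided 1% gives 0.990 and 0.983. The nearest match to 0.998 is the exact t-test at one-sided 5% (0.998). All of these are high, and the present question does not depend on which was used.

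**2. The passages side by side.**

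| Question | What the text supports |
|---|---|
| Who performs a final VUA? | Both groups, under a single requirement in the Summary, with no condition on reaching the benchmark |
| Whose final VUA is scored? | Each student's (Procedure and training) |
| Is it the qualifying attempt? | Not stated outright. The benchmark is shown before training counts as complete, while the final VUA comes at the end of training and mirrors the baseline VUA. The Traditional arm has no qualifying attempt, so a requirement common to both arms is naturally a separate assessment |
| What does the analysis use? | Baseline and end-of-training performance (Statistical Analysis) |
| When does training end without the benchmark? | Not stated in the readable text |
| What is Traditional time in that case? | Whatever the PBP time turns out to be, since it is matched to it |

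Only the stopping time is truly absent. Once a non-qualifying resident's training does stop, the matching rule gives the Traditional arm its time, and the end-of-training requirement triggers the final VUA in both arms. Neither harmful rule (scoring the qualifying attempt, or dropping non-qualifiers) appears anywhere in the plan, and the second conflicts with scoring each student.

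**3. Could the case arise?** The documents give no failure rate. If each of 18 PBP residents independently has probability p of missing the benchmark (assumed), the chance of at least one is 1 − (1 − p)^18:

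- p = 1%: 0.165
- p = 2%: 0.305
- p = 5%: 0.603
- p = 10%: 0.850

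So the case cannot be dismissed as too rare to matter.

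**4. What if some final VUAs were simply missing?** Inputs are a difference of 6.6, SD 4, two-sided 1%, an exact t-test on end-of-training scores, and 18 per group at the start. The noncentrality is 6.6 / (4 × √(1/n₁ + 1/n₂)).

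| PBP / Traditional | Noncentrality | Power |
|---|---|---|
| 18 / 18 | 4.950 | 0.983 |
| 16 / 18 | 4.802 | 0.976 |
| 16 / 16 | 4.667 | 0.966 |
| 14 / 14 | 4.366 | 0.934 |
| 12 / 12 | 4.042 | 0.876 |

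Power stays near 0.88 even with six lost from each arm. This table covers precision only; it says nothing about selection, which step 2 addresses.

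**The case for a change.** The best argument for a change is that it is cheap and protects the main result. One or two sentences would say that the final VUA is a separate procedure, that all 36 residents perform it and are analysed as randomised, and when it takes place if training stops early. If a separate VUA had not been intended, the Background section says "it takes the trainee approx. 20 mins to complete the task", so 18 extra procedures would take 18 × 20 = 360 minutes, or 6 hours. A positive PBP result would then be safe from the charge that passing attempts had been selected. No analysis set is stated that would otherwise answer that charge.

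Part of this stands. The stopping time for a non-qualifier is not in the readable text, and step 3 shows that the case may well occur. The wording would be harmless and helpful. But most of it would write down what the Summary and the Procedure and training section already require. Putting a size on the bias needs a benchmark value, a cap on attempts and a split of the variance between and within residents. The documents give none of these, and the bias arises only under rules the plan does not contain.

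The knowledge point is weaker. Both arms have a summative assessment, which is the obvious common measure. Resits are nowhere mentioned, and the hypothesis is secondary to the error count.

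**Conclusion.** This is a gap in detail that the trial team would fill sensibly, not a flaw in the design. Followed as written, the plan yields one end-of-training VUA for each of the 36 residents, scored blind, with Traditional training time following actual PBP time. Under that reading the benchmark decides neither who is scored nor which attempt is scored, so the bias from this source is zero. If two PBP residents nevertheless had no final score, power would move from 0.983 to 0.976.

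The conclusion rests on three things: that the end-of-training VUA is separate from the qualifying attempt, which the text favours without saying so outright; that non-qualifiers are kept, as scoring each student implies; and that Figure 1, which could not be read, does not contradict this. Should the trial report show that qualifying attempts were scored or non-qualifiers left out, the question would reopen as a departure from the plan. No change to the plan follows.
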